Risks associated with the Study Treatment: Ramelteon has FDA approval for use in elderly patients with insomnia. However this agent has never been used peri-operatively in older patients undergoing general or regional anesthesia and we cannot be certain that it will be safe in this setting. Therefore the study aims to test safety of this agent compared to placebo; we will systematically collect daily information on adverse (AE) and serious adverse events (SAE) that occur in each arm of the study. The main potential risk is one of increased incidence of delirium due to the treatment intervention. Other risks associated with the use of ramelteon reported in product labeling include: 1) angioedema and anaphylactic reactions – this risk is extremely rare; 2) worsening of insomnia, or the emergence of new cognitive or behavioral abnormalities that may be the result of an unrecognized underlying psychiatric or physical disorder, such as worsening of depression (including suicidal ideation and completed suicides), hallucinations, bizarre behavior, agitation and mania; 4) amnesia, anxiety and other neuro-psychiatric symptoms may also occur unpredictably, including complex behaviors such as "sleep-driving" (i.e., driving while not fully awake after ingestion of a hypnotic) and other complex behaviors (e.g., preparing and eating food, making phone calls, or having sex) with amnesia for the event; 5) decreased testosterone levels and increased prolactin levels have been reported with long-term use; 7) the use is contraindicated in severe hepatic failure as evidenced by cirrhosis, ascites, portal hypertension and prolonged bleeding times; 8) also contraindicated with the concomitant use of fluvoxamine; and finally 9) caution is to be used when prescribing with other CYP enzyme active agents such as rifampin, fluconazole, and ketoconazole. Other less serious side effects that have been reported in clinical trials include somnolence, fatigue, dizziness, nausea and worsened insomnia.

The following is taken from the ramelteon package insert:

ADVERSE REACTIONS

The following serious adverse reactions are discussed in greater detail in other sections: Severe anaphylactic and anaphylactoid reactions [see Warnings and Precautions (5.1)] Abnormal thinking, behavior changes, and complex behaviors [see Warnings and Precautions (5.3)] CNS effects [see Warnings and Precautions (5.4)]

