a.7. Exogenous Melatonin and Delirium Prevention: findings are mixed. Two trials in postoperative patients used superphysiologic doses: the first using 7.5 mg melatonin orally the night prior to, and a second dose 90 minutes before surgery. Active treatment was compared to patients receiving two other agents or no drug at all. A placebo was not used. The new occurrence of delirium on days 0-3 in the groups with no drug treatment vs. melatonin was 33% vs. 9%, respectively. ⁵⁷ The second was a recently published placebo-controlled RCT, testing oral doses of 3 mg of melatonin, administered for 5 consecutive nights in 378 older patients (mean age 84 years) undergoing hip fracture repair. This trial demonstrated neither delirium preventive effect (55/186 or 30% among melatonin group vs. 49/192 or 26% in the placebo) nor any functional differences at 3 months. ⁵⁸ Secondary analysis revealed that patients treated with melatonin, had fewer episodes of delirium lasting longer than 2 days, compared to placebo. ⁵⁸ Another placebo-controlled RCT was conducted in a medically ill patient population aged 65 and older using a physiologic dose of 0.5 mg of melatonin at bedtime for up to 14 days during a medical hospitalization. ⁵⁹ The delirium prevalence in placebo vs. melatonin (31% vs.12% respectively; p<0.02) resulted in an absolute risk reduction of 15.6% (NNT = 6.4).

a.8. Advantages of Ramelteon – include quality control and longer drug effect. Unlike melatonin, which is considered a dietary supplement, ramelteon is an FDA-regulated pharmaceutical. Inadequate comparability of biologic availability of melatonin, between different manufacturers and even between batches from the same company, has been cited as a major barrier to studying the effects of exogenous melatonin in clinical trials. ³⁶ As a regulated drug, ramelteon,

has distinct advantages with respect to quality control and comparable melatonergic activity. Furthermore a biologically active metabolite M-II contributes to a longer total drug effect of 5 hours compared to 1- 2 hours for melatonin.^{39,60}

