Choice of dosing times: include three consecutive evenings: 1) prior to surgery, 2) the night of surgery or POD 0 and 3) POD 1. The preoperative administration of ramelteon is designed to correct melatonergic deficiencies observed immediately following surgery and to enhance circadian rhythm and sleep effects.⁵⁴ Participants who are admitted to hospital the night before surgery will have study assigned medication administered by clinical staff, similar to the procedure for POD 0 and POD 1 doses. Participants undergoing elective surgery are given the first dose of medication at their preoperative study visit with instructions to take it the night before surgery. Study personnel will contact to remind the participant. Lack of adherence to self-administration of medication has been described as a barrier in the literature.⁷² Serving as a biologic tracer, 100 mg of riboflavin (Vitamin B₂) will be added to both the active agent and placebo of doses to be self-administered

outside of the hospital. Since riboflavin fluoresces under UV light, a urine sample obtained in the OR at the time of catheterization, will be sent for quantitative fluoroscopy using a cutoff of > 900 ng/ml as evidence of adherence. Replacement recruitment will be completed for any participants with urine samples negative for riboflavin.

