Randomization: A statistician ([name]) will be responsible for design, implementation, and maintenance of randomization procedures that assign participants to active pharmaceutical or placebo. Since preoperative cognitive impairment is consistently and strongly associated with the development of postoperative delirium, our randomization process will stratify by preoperative MMSE exam score to ensure balanced allocation (MMSE score 24/30 - 30/30 and 15/30 - 23/30). Under supervision of the statistician, research pharmacy staff who have no contact with the patient or clinical staff will randomize participants using a computer program, utilizing dynamic allocation probabilities to balance the two groups on the dichotomous MMSE variable.

Masking Procedures: The research pharmacy staff will prepare the active treatment (ramelteon 8 mg) and placebo using identical gel caps containing 100 mg riboflavin for doses to be self-administered outside of the hospital. No riboflavin will be added to study doses to be administered by hospital nursing staff. Once randomized, the assigned agent will be labeled with the patient's name and medical record number with the administration instructions consistent with hospital policy. No markings will indicate identity of the agent. Participants admitted on the day of surgery will receive the assigned study medication (active treatment/placebo) at the study visit prior to surgery. For all inpatient doses clinical nursing staff will administer medication each evening (8-10 pm). Administration will be documented in the clinical electronic medication record and adherence closely monitored by research staff.

Concomitant Medications: All medications except those enumerated in exclusions will be allowed.⁶⁰

Choice of Clinical Site and Feasibility of Recruitment: A total of 198 infection-free inpatients ≥ 65 years of age, underwent total hip or knee arthroplasty or revision under general anesthesia between 01/01/14-12/31/14 at JHBMC. The median (IQR) ASA physical status score and median surgical duration (IQR) was 3 (3-3) and 172 (122-216) mins. respectively, reflecting significant comorbidity and lengthy surgical times, consistent with high postoperative delirium risk likely to be at least 30%.⁵⁸

b. Study duration and number of study visits required of research participants.

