The inclusion of a placebo treatment is critical in helping advance our understanding of the effects (both positive and negative) of ramelteon exposure. Placebo comparison is the only way that we can understand what is likely due to ramelteon and what is not.

f. Definition of treatment failure or participant removal criteria.

All consented participants will be retained in the study. Participants with no evidence of riboflavin in the urine sample as tested by fluorescence prior to surgery (i.e. evidence of non-adherence to the first dose of study agent) will continue in the study, receiving second and third doses of study agent, and undergoing delirium outcome measures at all time points; however recruitment will continue until 80 participants with documented adherence to the first doses of study agent is attained. Primary analysis will be intent to treat with all randomized subjects included in the analysis; secondary analysis will include only patients with documented adherence all 3 doses of study medication (a per protocol analysis).

Participants who have their surgery canceled after they have been randomized and who are likely to have surgery in the future will be considered "suspended" from the study. These participants will continue in their assigned condition. A new baseline will be completed prior to their new surgery date to establish that they continue to meet inclusion criteria. The team will proceed with the protocol pre- and postoperatively as assigned during the original randomization. If the participant takes any of the study medication prior to the original surgery, a minimum of 7 days between initial study dosing and the re-initiation of the protocol is required to ensure sufficient time to wash out. If the rescheduled surgery occurs less than 7 days after original dosing, the participant will be excluded from the study.

g. Description of what happens to participants receiving therapy when study ends or if a participant's participation in the study ends prematurely.

Patients will be thanked for their help with the study and will be advised to call the PI with any questions.

5. Inclusion/Exclusion Criteria

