Participants and Recruitment: Eligible patients at JHBMC, identified from the surgical scheduling roster (after obtaining HIPAA waiver) and/or from referral by the patient's surgeon will be approached. Upon receiving informed consent from the patient or their legally authorized representative (LAR), a MMSE⁷⁵ and delirium assessment (see below) will determine eligibility. A similar recruitment procedure is employed in the ongoing STRIDE study at the JHBMC. Both elective and emergency surgeries will be eligible. Recruitment of ethnic and racial minority participants will be a priority.

Inclusion Criteria: 1) Planned orthopedic surgery and inpatient stay following surgery; 2) Age \geq 65 years; 3) MMSE \geq 15 before surgery; 4) Can understand, speak, read and write English.

Exclusion Criteria: 1) Delirium diagnosis by Confusion Assessment Method⁷⁶(CAM) at baseline; 2) Unable to give informed consent (as tested for with the consent questionnaire during telephone screening and during baseline visit) due to cognitive impairment and a suitable LAR cannot be identified; 3) Declines participation; 4) Current medications that include: a) ramelteon, b) melatonin, c) fluvoxamine, d) rifampin, e) ketoconazole, or f) fluconazole; 5) History of ramelteon or riboflavin intolerance; 6) Heavy daily alcohol intake by medical record or history 7) Current moderate to severe liver failure (as defined by Charlson criteria⁸²); 8) Evidence of Systemic Inflammatory Response Syndrome (SIRS) as measured by \geq 2 criteria;⁷⁷ or 9) Presence of a condition that in the opinion of the PI might compromise patient safety if enrolled in the study.

6. Drugs/ Substances/ Devices

a. The rationale for choosing the drug and dose or for choosing the device to be used.

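### Riboflavin from other sources is neither excluded nor recorded, so the urine tracer can class a participant who missed the home dose as adherent

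*Combined protocol and SAP*

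**What the plan says.** Section 4.a (Masking Procedures) specifies "identical gel caps containing 100 mg riboflavin for doses to be self-administered outside of the hospital"; doses given by hospital nurses carry no tracer and are documented in the medication record. Under Choice of dosing times, urine collected in the operating room "will be sent for quantitative fluoroscopy using a cutoff of > 900 ng/ml as evidence of adherence", and "Replacement recruitment will be completed for any participants with urine samples negative for riboflavin". Section 4.f adds that "recruitment will continue until 80 participants with documented adherence to the first doses of study agent is attained". That section, however, describes the non-adherent as those whose urine shows no sign of riboflavin, and does not repeat the cutoff.

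On other sources of riboflavin, three rules matter:

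- Section 5, exclusion 4: "Current medications that include: a) ramelteon, b) melatonin, c) fluvoxamine, d) rifampin, e) ketoconazole, or f) fluconazole".
- Section 5, exclusion 5: "History of ramelteon or riboflavin intolerance". This is the only eligibility rule that mentions riboflavin, and it concerns intolerance, not current intake.
- Section 4.a, Concomitant Medications: "All medications except those enumerated in exclusions will be allowed".

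The assessment table in Section 7.a lists no urine sample before the first dose and no vitamin or supplement history. No reason is given why 900 ng/ml separates the tracer from other sources.

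**The concern.** A tracer shows that the capsule was swallowed only if nothing else could produce the same reading. The plan does not secure that. The exclusion list does reach supplements: it names melatonin, and Section 3, item a.8 says "Unlike melatonin, which is considered a dietary supplement, ramelteon is an FDA-regulated pharmaceutical". The tracer substance itself is not covered.

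The test result carries weight. It decides who is replaced, when the count of 80 is reached, who enters the second, first-dose-adherent analysis (Section 7.c), and whether a self-administered first dose counts in the per-protocol set (Section 4.f). It also feeds the count of 40 adherent participants, one of two alternative triggers for the safety board's review (Section 7.d). Section 3, item b.3 presents assured first-dose adherence as a distinctive strength. Section 4.a names poor adherence to self-administered medication as a known barrier and plans to enrol people with mild to moderate dementia. In addition, the recovery-room outcome follows the first dose only, so later doses cannot make up for a missed one at that time point.

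**Working it through.** **1. The plan's own power figures.** Inputs from Section 7.c: 40 per arm, alpha 0.05 (two-sided assumed), 30% delirium on placebo against 3% or 6% on ramelteon.

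- Pooled z: power = Φ{[|p1 − p2| − 1.96·√(2p̄(1 − p̄)/n)] / √([p1(1 − p1) + p2(1 − p2)]/n)}.
- 30% vs 3%: (0.27 − 0.163)/0.0773 = 1.39, power 0.917. The plan states above 0.90.
- 30% vs 6%: (0.24 − 0.168)/0.0816 = 0.88, power 0.810. The plan's 0.84 is matched by the arcsine method (0.844) and the unpooled z (0.837).

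The sample-size arithmetic is therefore not in dispute. Pooled z is used below only to show the change.

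**2. Share wrongly counted as adherent.** Three inputs are needed and the documents give none of them, so they are assumptions: u = share missing the home dose; s = share of those with another riboflavin source; f = share of those above 900 ng/ml. Then

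m = u·s·f / (1 − u + u·s·f).

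| u | s | f | m | of 80 |
|---|---|---|---|---|
| any | any | 0 | 0 | 0 |
| 10% | 20% | 50% | 1.1% | 0.9 |
| 20% | 40% | 50% | 4.8% | 3.8 |
| 20% | 60% | 50% | 7.0% | 5.6 |
| 20% | 40% | 100% | 9.1% | 7.3 |
| 30% | 60% | 50% | 11.4% | 9.1 |
| 30% | 60% | 100% | 20.5% | 16.4 |

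Middle case: 0.20 × 0.40 × 0.50 = 0.04, and 0.04/(0.80 + 0.04) = 4.8%. The counts of 80 assume that every first dose is self-administered. Any nurse-given first dose lowers them.

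**3. Dilution of the adherent-set analysis.** If misclassified ramelteon participants lose all benefit, the ramelteon rate becomes p(1 − m) + 0.30m. For p = 6% and m = 5% this is 0.057 + 0.015 = 7.2%.

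| m (of 40 on ramelteon) | power, 30% vs 3% | power, 30% vs 6% |
|---|---|---|
| 0 | 0.917 | 0.810 |
| 2.5% (1) | 0.897 | 0.783 |
| 5% (2) | 0.875 | 0.755 |
| 10% (4) | 0.823 | 0.696 |

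The plan's rates refer to postoperative days 1 and 2. For those days loss of all benefit is a worst case, because the second and third doses are still given.

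**4. Early stop.** The number of home-dosed participants needed to reach the count is 80/(1 − u + u·s·f). In the middle case this is 80/0.84 = 95, against 80/0.80 = 100 with a test that makes no such errors.

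**The case against.** The strongest reply is that the mechanism rests on facts outside the documents. They mention no vitamin product, no supplement dose and no urine level after one. The test is quantitative, with a stated cutoff against a 100 mg tracer, so a low-dose product, or one taken well before the sample, may stay below it. The honest lower bound is zero. Reminder calls should reduce missed doses. Participants admitted the night before surgery are outside the issue. Screening for melatonin already implies some question about supplements. All of this stands and limits the size. None of it supplies the missing rule for reading a positive test.

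A reader might infer more than the documents support:

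- *That any vitamin user passes the test.* The Section 4.a cutoff does not allow that inference. Only the looser wording in Section 4.f would, if read literally.
- *That the primary result is biased or could show false efficacy.* The primary analysis takes everyone randomized. Both arms carry the tracer, so misclassification should not depend on arm, and the expected effect is a shift toward no difference in the adherence-based analyses.
- *That the interim review is compromised.* The count of 40 is one of two triggers, whichever comes first. A few extra counts could change its timing at most.

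Refusing to count every supplement user would also be out of proportion. Suppose 30 of 100 home-dosed participants took enough to exceed the cutoff and 20% of participants missed the dose. Then 30 × 0.80 = 24 of those 30 would be true adherers, discarded to remove 6 false ones.

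**Conclusion.** The gap is real but modest. For self-administered first doses, a positive urine result cannot separate the capsule from a comparable riboflavin intake elsewhere, and the plan neither restricts nor records such intake for that purpose. How often this matters cannot be settled from the documents. Under the assumed rates the share is 0 to roughly 10% of the counted 80, with a middle case near 4 people, and higher only when frequent missed doses combine with common supplement use that often passes the cutoff.

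The first-dose-adherent and per-protocol analyses are diluted; in the middle case about 2 of 40 ramelteon participants are affected, and power falls by about 4 to 6 points if they lose all benefit. Recruitment also ends slightly early. That trims the total randomized relative to an error-free test, but not below 80, and membership of the intent-to-treat set remains by randomization.

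**What to change.** 1. At the baseline visit, and again in the reminder call already planned, record use of riboflavin-containing vitamins or supplements.
2. In the adherence definition (Sections 4.a and 4.f), flag a value above 900 ng/ml in a reported user as *tracer not conclusive*.
3. Repeat the first-dose-adherent and per-protocol analyses without the flagged participants, as a sensitivity analysis.
4. In Section 4.f, state non-adherence by the 900 ng/ml cutoff, so that it agrees with Section 4.a.
5. If the sponsor also wants participants to avoid such products before the sample, reconcile this with the statement in Section 4.d that no existing treatment is discontinued.

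The cost is one question asked twice, one line in the definition and one extra analysis, with no new visit or assay. The downside is that a few participants in the adherent set carry a less certain status, and the sensitivity analysis is somewhat smaller.

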We propose a proof-of-concept (phase 2) double-blind randomized placebo-controlled trial to evaluate the efficacy and short-term safety of ramelteon for the prevention of postoperative delirium in a high-risk group of patients, 65 years and older, with MMSE²⁵ scores ≥ 15 , planned orthopedic surgery. Our prior work demonstrates the feasibility of conducting a prevention trial in this population, using state-of-the-art delirium detection and diagnosis methodology.^{5,25} Should this preliminary trial, show evidence of efficacy and adequate safety, then a phase 3 trial will be proposed.

Our group has demonstrated that an early predictor of subsequent delirium is the presence of delirium immediately upon recovery from general anesthesia in the post anesthesia care unit (PACU).^{5,26,27} The proposed trial will incorporate assessment of PACU delirium as a means of early delirium detection in helping to determine the efficacy of the ramelteon intervention.

2. **Objectives (include all primary and secondary objectives)** The proposed trial will involve administering 8 mg ramelteon orally (1 dose preoperatively and 2 doses postoperatively) or placebo in 80 older-aged patients to test the following:

Specific Aim 1 (primary outcome): To compare delirium incidence and severity between ramelteon and placebo using the DSM 5 criteria by expert panel consensus.

Hypothesis 1: Compared to placebo, ramelteon will be associated with a) a lower incidence and severity of postoperative delirium immediately upon recovery from anesthesia in the PACU, and b) with a lower incidence and severity of delirium on postoperative day (POD) 1 and POD 2.

Specific Aim 2 (safety outcome): To compare adverse events (AEs) and serious adverse events (SAEs) between ramelteon and placebo.

Hypothesis 2: Ramelteon will have an adequate safety profile in this postoperative cohort, sufficient to support conducting a larger prevention trial. Specifically, compared to placebo, ramelteon will not be associated with increased incidence of postoperative delirium or with increased adverse side effects including fatigue, headache and next day somnolence during the treatment episode.

3. Background (briefly describe pre-clinical and clinical data, current experience with procedures, drug or device, and any other relevant information to justify the research)

a. Significance:

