b.4. Summary of Innovation: This exploratory study is a novel approach to preventing postoperative delirium in older patients with and without cognitive impairment – a condition for which there is no prevention and little translational inquiry. Older individuals undergoing surgery, do so in the hopes of improving quality of life. Delirium prevention following surgery will significantly improve independence, well-being and decrease institutionalization. A widely available, generally safe intervention (ramelteon) would be exciting, novel, guiding translational inquiry to test important new mechanistic models of postoperative delirium.

4. Study Procedures

- a. Study design, including the sequence and timing of study procedures (distinguish research procedures from those that are part of routine care).

Overview: This randomized, masked, controlled trial is designed to evaluate the short-term safety and efficacy of peri-operative, orally administered 8 mg of ramelteon for the prevention of postoperative delirium; 80 delirium-free participants (n=40 per arm) ≥ 65 years of age, infection free and undergoing orthopedic surgery and post-procedure inpatient admission, will be randomized to ramelteon/placebo at the preoperative study visit, with administration of 3 nightly doses: one preoperatively and two following surgery while monitoring incidence of postoperative delirium. The following diagram outlines the proposed study timeline. All activities outlined in yellow indicate research activities while white background indicates routine clinical care.

Timeline of Clinical Course and Study Assessment (not to scale)

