Choice of study population and outcome measurement time points: Delirium, diagnosed early in recovery from anesthesia, is very common in older adults (45% after recovery from general anesthesia) and predicts delirium in the subsequent postoperative course.^{5,26,27,73} This finding runs contrary to the view that postoperative delirium cannot be diagnosed unless a period of lucidity has occurred following recovery from anesthesia, and that commonly observed confusion and uncooperativeness upon recovery are benign emergence phenomena.⁷⁴ Since **our previous work suggests that the syndrome, regardless of its attribution, predicts delirium in the days following surgery as well as measurable changes in cognitive function,**⁵ we have included two time periods of delirium incidence as our primary outcome: 1) in the PACU after recovery of arousal, hemodynamic, and respiratory function after anesthesia, as measured by Aldrete score \geq 8;⁷⁴ and 2) during POD 1 and 2 independent of status in the PACU. This will allow for the study of preoperative ramelteon on immediate recovery and during the traditionally described delirium incidence in the days following surgery. For participants who discharge early from the hospital (prior to POD 2), delirium assessment will be conducted via telephone. While longer-term follow-up beyond POD 2 is desirable, it is difficult to complete in all patients in this preliminary study due to an institutional trend toward early post-surgery discharge. We plan to recruit patients with significant cognitive impairment at baseline (mild to moderate dementia) by including participants with Mini Mental State Exam (MMSE) scores \geq 15.⁷⁵ Based upon our previous work, distribution of MMSE scores of 24-30, 15-23, and < 15 prior to surgery for this population will be 50-60%, 25-33% and 7-25% respectively. Participants who score below this cut-off are increasingly difficult to test, making delirium diagnosis difficult.

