Outcome Measure Specific Aim I – State-of-the-Art Delirium Assessment and Diagnosis: Well-trained research staff will conduct delirium assessments at baseline, to exclude cases of prevalent delirium, and at three later time points (see Figure and Table). This assessment includes: (1) face to face standardized interview of the patient regarding experiences, (2) standardized cognitive testing including the MMSE⁷⁵ and the abbreviated Digit Span,⁸⁰ (3) history from family/friends familiar with the patient’s cognitive baseline, (4) interview of nursing and other medical staff caring for the patient, and (5) review of medical records for evidence of behavioral disturbances and symptoms in previous 24 hours. Information on sleep disturbance is sought from all sources and is a symptom of delirium. Assessors will rate the CAM⁸¹ and the Delirium Rating Scale-Revised ’98 (DRS-R98)⁶² for the prior 24 hours and describe the patient’s behavior and mental state in a written narrative. If a patient is intubated the CAM-ICU⁸² will be administered to determine delirium status. Patients who are comatose will be documented as such. (Preliminary data suggests that this is a rare occurrence <1%) Final adjudication of delirium diagnosis is derived after all data is presented to a panel of expert delirium diagnosticians ([name]).

The primary diagnosis of delirium is based upon meeting all DSM-5 criteria (see appendix), and is determined by consensus of the expert panel - a method currently employed by this group of co-investigators in the STRIDE study.

A second outcome measure will be analyzed using the continuous variable of delirium severity derived from the DRS-98R severity measure.

Outcome Measure Specific Aim II- Adverse Events: All adverse events (AE and SAE) will be collected from the medical record and daily patient assessment using a customized instrument (“Health Questionnaire”) which will systematically probe for known side effects (fatigue, headache and next day somnolence) (see Protection of Human Subjects). Assessment of Outcome and Covariates:

Table: Timing and Content of Patient Assessments

Assessments	Administration	Collection Instrument and Source
Cognition	Preoperative, PACU POD 1 and 2	Mini Mental State Exam Abbreviated Digit Span: Forwards and Backwards
Delirium	Preoperative, PACU, POD 1 and 2	CAM (full) ⁸³ after patient exam + proxy/medical record review or CAM-ICU if intubated; DRS-98R (severity measure)

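### PACU and POD 1–2 delirium incidence are both primary under one final alpha of 0.05, and no rule says whether success needs one of them or both

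*Combined protocol and SAP*

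**What the plan says.** Section 4a, on the choice of study population and outcome time points, states "we have included two time periods of delirium incidence as our primary outcome". The periods are the PACU, and POD 1 and 2 whatever the PACU status. The reason given for the first is "This will allow for the study of preoperative ramelteon on immediate recovery".

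Specific Aim 1 in section 2, labelled the primary outcome, reads "To compare delirium incidence and severity between ramelteon and placebo using the DSM 5 criteria by expert panel consensus". Hypothesis 1 says that ramelteon "will be associated with a) a lower incidence and severity of postoperative delirium immediately upon recovery from anesthesia in the PACU, and b", followed by the same statement for POD 1 and POD 2.

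Section 7c (Analysis 1) fits a logistic model to PACU delirium and a separate Markov logistic model, which conditions on the previous day's mental status, to POD 1 and 2. Section 7d sets alpha at 0.001 for the interim look and 0.05 for the final efficacy analysis. Section 4f adds "Primary analysis will be intent to treat with all randomized subjects included in the analysis".

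The incidence power statements in section 7c concern POD 1 or 2 only, with 30% on placebo and 40 per arm: above 0.90 against 3%, and 0.84 against 6%. PACU delirium and success on both periods have no power figure.

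**The concern.** Two separately tested primary endpoints share one alpha, and the plan does not say how the two results combine. It gives no split, no testing order, and no statement that one suffices or that both are needed. Hypothesis 1 joins the periods with the word *and*, but as an expectation, not as a rule for declaring success.

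The opening section says that should the trial "show evidence of efficacy and adequate safety, then a phase 3 trial will be proposed". If a result on either period can be that evidence, 0.05 understates the chance of a false lead. If both periods are needed, 0.84 overstates the chance of success wherever the PACU test has limited power. With the rule unwritten, it could be settled after seeing which period reached significance.

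**Working it through.** **1. The plan's own figure.** Inputs from section 7c: 30% vs 6%, 40 per arm, alpha 0.05. Sidedness is not stated. Two-sided, unpooled normal formula:

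- SE = √(0.30×0.70/40 + 0.06×0.94/40) = 0.0816
- power = Φ(0.24/0.0816 − 1.96) = Φ(0.98) = 0.837

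The exact power of the uncorrected chi-square (pooled z) test is 0.845. Both agree with the stated 0.84. A one-sided pooled calculation gives 0.887, so two-sided testing is inferred. The 0.84 is thus an unadjusted comparison of two proportions.

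**2. Range for the correlation.** The protocol says only that PACU delirium predicts later delirium. I take 0 as the lower end. The upper end is the largest correlation two binary outcomes can have at 45% (the PACU rate in section 4a, after general anesthesia) and 30%:

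- (0.30 − 0.45×0.30)/√(0.45×0.55×0.30×0.70) = 0.165/0.228 = 0.72

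In simulated trials with unadjusted tests, the correlation between the test statistics equalled that between the outcomes. The planned Markov model may behave differently, so 0 to 0.72 is an assumption.

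**3. If either period counts, no true effect.** At correlation 0:

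- two-sided: 1 − 0.95² = 0.0975
- in ramelteon's favour: 1 − 0.975² = 0.0494

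For other correlations, the bivariate normal with critical value 1.96:

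| Correlation | At least one, two-sided | At least one, favouring ramelteon |
|---|---|---|
| 0 | 0.0975 | 0.0494 |
| 0.5 | 0.0907 | 0.0454 |
| 0.72 | 0.0825 | 0.0412 |

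Simulated null trials (400,000 per setting, 40 per arm) gave 0.101 falling to 0.086 two-sided. They run slightly higher because the pooled test at a 45% rate has a size of about 0.056.

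The lower end depends on the assumed rates. At a PACU rate of 35% the correlation limit is (0.30 − 0.35×0.30)/√(0.35×0.65×0.30×0.70) = 0.89, and the two-sided figure there is 0.071.

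**4. If both are required.** With no effect on either, the chance of both favouring ramelteon is 0.0006 to 0.009. With no effect on one, it cannot exceed 0.025. There is no inflation.

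Joint power uses exact single-test powers, with POD 1–2 at 0.845 (30% vs 6%) and PACU effects that are my assumptions. The lower figure takes the tests as independent, for example 0.845 × 0.569 ≈ 0.48. The upper takes the highest feasible correlation in each arm.

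| PACU, placebo vs ramelteon | PACU test alone | Both significant |
|---|---|---|
| 45% vs 9% (80% lower) | 0.972 | 0.82–0.84 |
| 45% vs 22.5% (halved) | 0.569 | 0.48–0.54 |
| 45% vs 30% | 0.285 | 0.24–0.28 |

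**5. Does 0.84 describe the planned POD 1–2 test?** Not in two respects.

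- *Population.* The 0.84 is for 80 adherent participants; the primary analysis also includes first-dose non-adherers. Suppose they gain nothing and recruitment continues to 40 adherent per arm. At 10% non-adherence, n = 40/0.9 ≈ 44 per arm, the ramelteon rate is 0.9×6% + 0.1×30% = 8.4%, and exact power is 0.77. At 20%, n = 50, the rate is 0.8×6% + 0.2×30% = 10.8%, and power is 0.69. Non-adherers still receive the later doses, so this is a worst case.
- *Model.* Taking PACU status as the previous status for POD 1 (an assumption), simulations of the Markov model with 30% vs 6% gave power of about 0.75 with no PACU effect, 0.55–0.64 with PACU delirium halved and 0.34–0.62 with it down 80%. A PACU benefit is partly conditioned away. These are rough, since some fits fail at this sample size.

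**The case against.** The strongest reply is that this is a small early trial. The protocol calls it proof-of-concept and a pilot, and writes "This exploratory study is a novel approach to preventing postoperative delirium in older patients". Phase 3 is not tied to a p-value, the 0.05 appears under early stopping, and the either-counts error in ramelteon's favour stays below 0.05. This stands as a limit on the consequence. It does not supply the missing rule: the plan sizes the trial by power, sets a formal final alpha and makes phase 3 conditional on evidence of efficacy.

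A second reply is that *and* in Hypothesis 1 already requires both. That reading is possible, but then the power of the decision is unreported.

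A third is that the correlation and the PACU effect are assumed. They are, because the plan gives neither. The PACU rate is uncertain too, since section 8a refers to general or regional anesthesia.

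A reader might also infer that severity is ranked inconsistently, because section 7a says "A second outcome measure will be analyzed using the continuous variable of delirium severity". The text does not support this. The sentence stands under the heading for primary outcome variables, section 7b does not list severity, and Aim 1 includes it. The likelier reading is a second measure within the primary aim. The false-positive figures count only the two incidence tests, so they do not cover every route to a positive claim.

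**Conclusion.** The gap is real and modest. If either period suffices, the false-positive chance is about 0.08–0.10 two-sided and 0.041–0.049 in ramelteon's favour, assuming correlation 0 to 0.72 at rates of 45% and 30%. It is lower if the rates are closer together and the correlation near its limit. If both are needed, error is controlled and joint power ranges from about 0.24 to 0.84 over the PACU effects examined.

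Two stronger conclusions are tempting. One is that the trial as planned has a 10% false-positive rate. The documents do not support that, because they never adopt an either-counts rule. The other is that making POD 1–2 the sole primary endpoint keeps the stated 0.84. They do not support that either: 0.84 is for an unadjusted comparison among adherent participants, while the planned analysis is intent-to-treat with a Markov model.

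**What to change.** Before unblinding, name cumulative delirium incidence on POD 1 or 2, the quantity used in the power calculation, as the single primary endpoint at two-sided 0.05 in the intent-to-treat population. Test it by a direct between-arm comparison, or a logistic regression that does not condition on PACU or previous-day status. Keep the Markov model as supportive.

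Make PACU incidence and DRS-R98 severity key secondary endpoints, tested only if the primary succeeds, with Holm (smaller p-value at 0.025, the other at 0.05). Otherwise report both as estimates with confidence intervals.

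If the team wants PACU to stay primary, one sentence closes the gap: either Holm across the two incidence tests, or both required at 0.05 each, with the matching power. Under Holm, the 30% vs 6% comparison has exact power 0.75 at the first step. Under both-required, the joint powers above apply.

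The cost is wording only, with no added patients. PACU and severity lose primary rank and cannot alone support an efficacy claim, and PACU was included to study the preoperative dose. With 40 per arm and unadjusted incidence tests, power changes as follows:

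| Endpoint | At 0.05 | First Holm step (0.025) | First step, after the primary succeeds |
|---|---|---|---|
| PACU halved | 0.57 | 0.46 | 0.39–0.45 |
| PACU 80% lower | 0.97 | 0.94 | 0.80–0.83 |
| Severity (section 7c means and SDs) | 0.84 | 0.76 | 0.64–0.71 |

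The last column would be lower if intent-to-treat dilution reduces power for the primary. The amended text should give power for the chosen test and population, not carry 0.84 over.
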